### 9.5 Exploratory Endpoints

We expect to have all patients evaluated for correlatives at least at baseline, and it is reasonable to expect at least 10 patient samples per timepoint/technique to interpret potential trends. In the event that insufficient bone marrow is collected, blood samples may be used (30 mL per collection), provided that a minimum of 1g/L of circulating blasts are present on the differential of the CBC.

#### 9.5.1 Changes in 2HG Levels

The Mann-Whitney U test will be used to test for differences in post-treatment plasma 2HG concentrations between patients with a response to treatment and those without. We will also test for differences in  $\Delta$ 2HG (defined as pre-treatment minus post-treatment plasma concentration) between patients with a response to treatment and those without. Differences with  $p \leq 0.05$  will be considered significant. The area under the receiver operating characteristic curve (ROC AUC) will be calculated to determine the cutoff value of the  $\Delta$ 2HG difference. The optimal cutoff value will be determined at the point on the ROC curve at (sensitivity + specificity - 1) is maximized (Youden index).

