## 9. STATISTICAL CONSIDERATIONS

### 9.1 Study Design/Endpoints

#### 9.1.1 Study Design

This is an open-label study of olaparib in advanced relapsed or refractory IDH1/2-mutant AML and MDS. The study will have 4 arms. Arm 1 will include patients with relapsed or refractory AML with no prior exposure to IDH inhibitors (inhibitor naïve). Arm 2 will be composed of patients with relapsed or refractory AML with prior exposure to IDH inhibitors. Arm 3 will include patients with relapsed or refractory MDS with no prior exposure to IDH inhibitors (inhibitor naïve). Arm 4 will be composed of patients relapsed or refractory MDS with prior exposure to IDH inhibitors.

The effect of PARP inhibitors is dependent on 2-HG levels, and 2-HG levels are high in both IDH inhibitor naïve patients, as well as in patients who relapse after IDH inhibitors. While 2-HG levels are suppressed in patients actively on IDH inhibitors (independent of response, which discourages concomitant administration), in patients who relapse after IDH inhibitors 2-HG levels are seen to increase despite continued IDH inhibitor therapy. This has been seen in numerous studies (*e.g.*, Intlekofer *et al.*, 2018). Therefore, we expect a rather similar efficacy of PARP inhibitors in both IDH inhibitor naïve and IDH inhibitor pre-treated patients.

For the null hypothesis, the CR rate is 30% in IDH inhibitor naïve AML patient, not for patients with previous IDHi exposure. For the MDS, population, the data for IDHi naïve patients are still limited and we will have a conservative estimate that the rate of response will be similar to AML. The null hypothesis for patients already treated with at least 1 line of therapy and an IDH inhibitor will be set at 5% given the absence of available options for either MDS or AML. Sample sizes and futility rules:

Cohort	H0	H1	Alpha 1 sided	beta	Sample size stage 1	Futility	Sample size total*	Efficacy
AML IDHi naïve	30	50	5	20	19	6 or less	39	17 or more
AML IDHi exposed	5	35	5	10	8	0	14	3 or more
MDS IDH I naïve	30	50	5	20	19	6 or less	39	17 or more
MDS IDHi	5	35	5	20	6	0	12	3 or more

exposed								
---------	--	--	--	--	--	--	--	--

The calculations are based on a Simon 2 Stage Minimax design.

\* without the drop-out rate of 15%

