## 9.3 Stratification Factors

Patients will be stratified based on prior exposure to IDH inhibitors. Both untreated and pre-treated cohorts will be evaluated independently from the statistical perspective. AML and MDS patients will also be analyzed separately.

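### Section 9.5.1 does not say how the four arms enter the 2HG responder comparison; pooling can confound it, and separate tests may be unusable in the exposed arms

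*Combined protocol and SAP*

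**What the plan says.** Section 9.5.1 is the only analysis plan for 2HG. It states that "The Mann-Whitney U test will be used" for comparing responders with non-responders on plasma 2HG after treatment. A second comparison uses the change in 2HG, "defined as pre-treatment minus post-treatment plasma concentration) between patients with a response to treatment and those without". The significance threshold is p at or below 0.05. A ROC AUC is then calculated, and one cutoff for the change is chosen by the Youden index. No arm, stratum or adjustment appears, and sidedness is not stated.

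Section 9.3 is general. It says "Both untreated and pre-treated cohorts will be evaluated independently from the statistical perspective" and, for disease, "AML and MDS patients will also be analyzed separately". It does not mention 2HG, and 9.5.1 does not refer to it.

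Section 9.1.1 sets hypothesis rates by exposure. For the null, "the CR rate is 30% in IDH inhibitor naïve AML patient", and MDS naïve patients are assumed similar. For exposed patients, "The null hypothesis for patients already treated with at least 1 line of therapy and an IDH inhibitor will be set at 5" percent. The alternatives are 50% (naïve) and 35% (exposed). Full arm sizes are 39 (AML naïve), 14 (AML exposed), 39 (MDS naïve) and 12 (MDS exposed).

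**The concern.** The text leaves two analyses open, and either could be chosen once the data are in.

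- **Pooled.** A single test and a single cutoff are the natural reading of 9.5.1 alone. Section 9.5 expects at least 10 samples per timepoint and technique, not per arm. If exposed patients respond less often and also have different 2HG, responders will differ from non-responders in 2HG because of the arm they come from, even with no link inside any arm.
- **Separate.** If 9.3 governs, there are four tests, two of them in arms of 14 and 12 patients.

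The documents give some reason to think that exposure could be linked to both variables. Section 2.3 allows that olaparib's effect may be blunted to some degree by an IDH inhibitor. Section 9.1.1 says 2HG is suppressed while patients are on these inhibitors, and I find no washout in sections 3.1 and 3.2 that names them. Under section 12.1, response is first assessed after Cycle 1 in naïve patients but after Cycle 3 in exposed patients, and 9.5.1 does not date the post-treatment sample.

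At stake is a spurious association, or no usable result, for plasma 2HG. It is the only biomarker that section 5.7 labels integrated.

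**Working it through.** **1. The plan's own figures.** Exact two-stage binomial calculations reproduce the 9.1.1 designs. One-sided alpha and power are 0.0455 and 0.804 (19/39, both naïve arms), 0.0286 and 0.905 (8/14), and 0.0179 and 0.822 (6/12). The plan gives no sample size or power for the 2HG test.

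**2. If arms are pooled.**

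Inputs from 9.1.1: arm sizes 39/14/39/12 and the tabled rates. These sizes sum to 104; the stated total of 94 is a separate matter.

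Assumptions:
- normal 2HG on a suitable scale, with exposed arms shifted by 0, 0.5 or 1 SD, because the documents give no 2HG values by arm;
- no 2HG–response link within any arm;
- response as in the composite CR rates;
- a two-sided 5% level and complete samples.

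For a group of n patients with m responders, let W be the responders' rank sum, E = m(n+1)/2 and V = m(n−m)(n+1)/12. The pooled test is Z = (W−E)/√V over all patients. The van Elteren test computes W, E and V within each arm k: Z = Σ[(W_k−E_k)/(n_k+1)] / √Σ[V_k/(n_k+1)²].

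Rejection rates in 6,000 simulated trials per row (simulation SE at 5%: √(0.05×0.95/6000) ≈ 0.3 percentage points):

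| Response naïve/exposed | 2HG shift | Pooled | Stratified | Mean pooled AUC |
|---|---|---|---|---|
| 50%/35% (targets) | none | 5.0% | 5.2% | 0.499 |
| 50%/35% | exposed, 0.5 SD | 6.4% | 5.4% | 0.516 |
| 50%/35% | exposed, 1 SD | 8.0% | 5.1% | 0.530 |
| 30%/5% (nulls) | none | 5.4% | 5.0% | 0.499 |
| 30%/5% | exposed, 0.5 SD | 8.4% | 5.0% | 0.536 |
| 30%/5% | exposed, 1 SD | 16.4% | 5.0% | 0.568 |
| 40%/40% | exposed, 1 SD | 4.8% | 5.0% | 0.500 |
| 50%/35% | MDS, 1 SD | 4.9% | 5.2% | 0.499 |
| 30%/5% | MDS, 1 SD | 4.8% | 5.0% | 0.498 |

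Both differences are needed. An AML/MDS shift alone does nothing at the tabled rates, because the two diseases share the same hypotheses within each exposure group.

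**3. Futility rules.** At a 5% response rate the exposed arms stop after stage 1 with probability 0.95^8 = 0.66 and 0.95^6 = 0.74, so fewer exposed patients enter the comparison. With the 9.1.1 stopping rules applied, the pooled rates at the nulls fall to about 7% (0.5 SD) and 11% (1 SD).

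**4. If 9.3 means separate tests.** Expected responders in the full exposed arms:
- at 35%: 14×0.35 = 4.9 and 12×0.35 = 4.2;
- at 5%: 14×0.05 = 0.7 and 12×0.05 = 0.6.

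With one responder among n patients, the smallest exact two-sided p is 2/n: 2/14 = 0.143 and 2/12 = 0.167. Significance is then impossible. The chance of 0 or 1 responder at a 5% rate is 0.95^14 + 14×0.05×0.95^13 = 0.85 for n = 14, and 0.88 for n = 12. At 35% it is 2% and 4%.

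**The case against.** The strongest reply is that 9.3 is a general rule and already settles the matter, so that no pooled test is planned. A reader might infer from 9.5.1 that an unstratified pooled test has been chosen. The documents do not establish that, and what stands is only that 9.5.1 is silent. But reading 9.3 into 9.5.1 leads to the small-arm problem in step 4.

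A reader might also infer that response rates differ by arm by design. They do not. The 30% and 5% are null benchmarks, and 9.1.1 expects rather similar efficacy in naïve and pre-treated patients. It also expects high 2HG in both groups, rising at relapse even on continued inhibitor. If either expectation holds, pooling does no harm. This objection stands and limits the size of the point.

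Much larger inflation can be produced. With 50% response in naïve and 10% in exposed arms, the pooled error is 28% at a 1 SD shift and 49% at 1.5 SD. The 10% is found nowhere in the plan, and the futility rules reduce these figures to 22% and 36%. They should not be quoted as the expected error. Incomplete post-treatment sampling, which section 9.5 allows for, would lower the inflation further.

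Finally, the objective is exploratory (1.3.1), the analysis sits under Exploratory Endpoints, and no go/no-go decision depends on it. That also stands.

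**Conclusion.** The point holds as a gap in specification. Section 9.5.1 does not say how arms are handled, and each of the two available readings is weak in plausible circumstances. Pooled, the false-positive rate is about 6–8% at the target rates and 8–16% at the null rates (about 7–11% with the futility rules), for assumed exposure shifts of 0.5 to 1 SD. It is about 5% if response or 2HG does not differ by exposure. Tested separately, the exposed arms would usually be uninformative if response is near 5%, and would have only four or five expected responders each at 35%.

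The figures rest on assumed 2HG shifts, full arm sizes except where futility is stated, and response taken as composite CR.

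A reader might infer a risk of a false claim that 2HG predicts response. The text does not support that: 9.5.1 tests post-treatment level and change, not a baseline predictor. Whether a baseline test should be added is a separate point. The priority is modest.

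**What to change.** In 9.5.1:

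1. Replace the Mann-Whitney test by the van Elteren rank test stratified by the four arms, for post-treatment and for change in plasma 2HG, and state how this relates to 9.3.
2. Report the AUC within each arm and combined over arms. Weights m_k(n_k−m_k)/(n_k+1) match the test, since W_k−E_k = m_k(n_k−m_k)(AUC_k−0.5).
3. Derive the Youden cutoff with arm taken into account, for example by maximizing a weighted average of the within-arm index, and not from a pooled curve.

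The cost is a few sentences. The arms already exist and no new data are needed. Arms with no responders contribute nothing, so at the null rates the exposed arms would add little. If the arms do not differ, the power loss is slight: about 81% against 83% for the pooled test in a simulated check. In every scenario run, the stratified test kept its error at about 4–6%.

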### 2.4.2 Integrated Biomarkers

#### 2.4.2.1 Peripheral blood and bone marrow 2HG levels

The main objectives of this assay are to: 1) correlate the chances of response to olaparib with baseline 2HG levels and 2) evaluate the longitudinal variations of 2HG levels as a marker of response to treatment and progression.

Based on our experience, as detailed in the background section, the “BRCAness” of IDH mutated patients is related to the exposure of the cell to 2HG. We hypothesize that patients with elevated levels of 2HG may have a better response to olaparib. We also want to confirm that olaparib is able to reduce the levels 2HG and maintain low levels of 2HG in treated patients.

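### The 2HG responder comparisons are not adjusted for baseline 2HG, so a significant delta-2HG cannot be read as a larger fall in responders

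*Combined protocol and SAP*

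**What the plan says.** Section 2.4.2.1 gives the 2HG assay two separate objectives: to "correlate the chances of response to olaparib with baseline 2HG levels", and to "evaluate the longitudinal variations of 2HG levels as a marker of response to treatment and progression". It adds a hypothesis, "We hypothesize that patients with elevated levels of 2HG may have a better response to olaparib", and a further aim: "We also want to confirm that olaparib is able to reduce the levels 2HG and maintain low levels of 2HG in treated patients".

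Section 9.5.1 is the only place that turns these into tests. It begins: "The Mann-Whitney U test will be used to test for differences in post-treatment plasma 2HG concentrations between patients" with and without a response. It then compares delta-2HG, "defined as pre-treatment minus post-treatment plasma concentration", between the same two groups. Differences at p of 0.05 or below "will be considered significant"; sidedness is not stated. A ROC curve and Youden index then give a cutoff for delta-2HG.

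No section specifies a relative or log scale, a baseline covariate, a test of baseline 2HG against response, or a within-patient test of change. Section 9.5.1 also does not say which of the scheduled samples (after Cycles 1, 3, 6, 9 and 12, and at end of treatment, per section 5.7) is the post-treatment one.

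**The concern.** A raw difference depends on where the patient started. With the same proportional fall, a patient whose baseline is twice as high shows twice the absolute fall. If responders also start higher, delta-2HG separates the groups even though the drug lowers 2HG by the same fraction in everyone. The post-treatment comparison has the same weakness, because a patient who starts high also tends to end high.

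The two objectives of section 2.4.2.1, baseline level and change, are therefore merged in the planned tests, and nothing in section 9.5.1 separates them. A report could state that 2HG fell more in responders, with a cutoff in concentration units, when the data show only that responders began higher. Plasma 2HG is the trial's integrated biomarker and ranks second in the section 5.7 priority list, so the result is likely to be used in planning later studies. The aim of confirming that olaparib lowers 2HG has no test that answers it, since both planned tests are between groups.

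**Working it through.** **Inputs from the documents.** The definition, the tests and the 0.05 level come from section 9.5.1. The possible link between baseline and response comes from section 2.4.2.1. Section 9.5 expects at least 10 samples per time point and technique; a naive cohort has 39 patients (section 9.1.1); the whole trial has 94 (section 9.2). The documents give no 2HG variance, effect size or power, so there is no stated figure to reproduce.

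**Algebra.** Let every patient's 2HG fall by the same fraction r. Then post = (1 - r) x pre, and delta = pre - post = r x pre. With r = 0.5, baselines of b and 2b give deltas of 0.5b and b, while log(pre/post) = log 2 for both. Since r is a constant, ranking patients by delta is the same as ranking them by baseline. Without noise, the Mann-Whitney test and ROC curve for delta are those for baseline 2HG. The same holds for the post-treatment level.

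**Simulation 1, proportional fall.** Assumed: log-normal baseline with log-SD 1, a 50% fall in everyone, log noise SD 0.4 on the post-treatment value, responder baseline higher by 0.5 to 0.8 log units, two-sided test at 0.05. Group sizes have about 30% responders: 3 + 7 = 10, 12 + 27 = 39, 28 + 66 = 94.

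| Responders vs non-responders | Raw delta significant |
|---|---|
| 3 vs 7 | 5-12% |
| 12 vs 27 | 20-44% |
| 28 vs 66 | 41-79% |

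At 12 vs 27 the planned post-treatment test is significant in 25-52%. The log ratio rejects in 4-6% at the two larger sizes. With no baseline shift, the raw difference also stays at or below about 5%.

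**Simulation 2, other inputs.** Assumed: log-SD 0.5 or 1.0, response odds ratio 2 or 3 per SD of log baseline, 35% responders, noise 0.2 to 0.4, a 50% fall in everyone. Raw delta is significant in 7-19% at N = 10, 23-74% at N = 39 and 49-99% at N = 94. Its mean AUC is about 0.61 to 0.75, against 0.49 to 0.51 for the log ratio. At N = 39 (odds ratio 3, log-SD 1.0, noise 0.3), common falls of 10%, 20%, 30%, 50% and 80% give 13%, 22%, 36%, 70% and 77%.

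**Simulation 3, equal absolute fall.** Assumed: baseline = 1 + log-normal (log-SD 1), a fall of 0.8 in everyone, log noise 0.4. Raw delta rejects in 5-8%. The log ratio is now the confounded measure: at a shift of 0.8 it rejects in 21% at 12 vs 27 and 45% at 28 vs 66.

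**Baseline adjustment.** Comparing log post-treatment 2HG by response, with log baseline 2HG as covariate, rejects in 4-6% in every setting tried under both kinds of fall.

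**The case against.** - **The artefact is conditional.** It needs a roughly proportional fall and a true link between baseline and response. Section 2.4.2.1 says only that such patients may respond better, and no section gives the scale of any fall. This stands. A reader might infer that delta-2HG is bound to differ by response, but the documents do not support that.
- **The log ratio is not neutral.** Simulation 3 bears this out. Section 2.1.1 notes that one form of 2HG arises from processes such as hypoxia, so part of the measured level may not respond to treatment. A reader might infer that changing to the log ratio is enough; it is not, and this is why baseline adjustment is the main remedy.
- **The post-treatment test would expose the misreading.** In the proportional scenario, responders' median post-treatment 2HG was higher in about 99% of the trials with a significant delta (12 vs 27). That would alert a careful reader. It does not separate level from change, because that test is itself driven by baseline.
- **The larger sizes are generous.** The 28 vs 66 case pools all 94 patients with complete pairs, while section 9.3 evaluates cohorts separately and section 9.5 counts on only about 10 samples. At that size false significance is uncommon. The expected AUC is still shifted.
- **A marker may carry baseline information.** Objective 1.3.1 and the second assay objective ask for association with response, not for an isolated drug effect. That is fair for prediction. It does not license describing the result as a larger fall.

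**Conclusion.** The point holds in a limited form. As planned, neither between-group test can distinguish a larger fall in responders from a higher starting level, and the ROC cutoff inherits the problem. If 2HG falls roughly proportionally and responders start higher, the raw difference is significant in about 5-12% of trials at 3 vs 7, 20-44% at 12 vs 27 and 41-79% at 28 vs 66. If the fall is the same in absolute units, raw delta is close to nominal, though the post-treatment test remains baseline-driven. All variances, shifts and effect sizes are assumptions. The gap in testing whether olaparib lowers 2HG does not depend on them.

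A reader might also infer that this threatens the trial's main result. It does not: the analysis sits under exploratory endpoints and enters no efficacy or stopping decision.

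**What to change.** In section 9.5.1:

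1. Make the responder comparison one of log post-treatment 2HG adjusted for log baseline 2HG, for example by linear regression, at each scheduled time point. Name end of Cycle 1 as the main one, since that plasma sample is mandatory in all arms (sections 5.1 and 5.7), and keep later time points for the longitudinal objective.
2. Report the log ratio alongside the raw difference, including for the ROC analysis.
3. Test baseline 2HG against response separately, which also serves the first assay objective.
4. Add a within-patient signed-rank test of log(pre/post), with a 95% confidence interval, for the aim of confirming that olaparib lowers 2HG.

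The cost is a little more analysis and revised wording; samples and assay are unchanged. One limit remains: the main simulations put noise on the post-treatment value, and error in the measured baseline would leave some residual dependence after adjustment. The change should be made before the 2HG data are analysed.

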The safety and efficacy will be evaluated by an independent data review committee at each critical step of the protocol. Given the patient population, we considered a potential drop-out rate of 15%. Expected monthly accrual is 3-4 patients per month, with a proposed total sample size of 94 patients, over 2 years.

Demographic information such as age and race will be tabulated. Descriptive statistics, including means, standard deviations, and ranges for continuous parameters, as well as percentages and frequencies for categorical parameters, will be presented. Adverse medical events will be tabulated. CTCAE Grade 3 and Grade 4 laboratory abnormalities will be listed.

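### The delta-2HG cut-off is chosen by maximising the Youden index with no correction or interval, so any accuracy quoted at that cut-off is biased upward, misleadingly so in small subsets.

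*Combined protocol and SAP*

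**What the plan says.** Section 9.5.1 plans three steps for plasma 2HG.

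- Mann-Whitney tests compare responders with non-responders on the post-treatment level and on delta-2HG, "defined as pre-treatment minus post-treatment plasma concentration) between patients with a response to treatment and those without". Differences with p of 0.05 or less "will be considered significant. The area under the receiver operating characteristic curve (ROC AUC) will be calculated".
- The ROC AUC is calculated.
- A delta-2HG cut-off is then set: "The optimal cutoff value will be determined at the point on the ROC curve" at which the Youden index peaks. This step is not made conditional on the tests.

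The section does not fix the post-treatment time point, although Section 5.7 lists plasma sampling after Cycles 1, 3, 6, 9 and 12 and at end of treatment. It does not say whether a high or a low delta-2HG is meant to indicate response, or whether cohorts are pooled. No validation set, cross-validation, bootstrap or confidence interval is given for the AUC or the cut-off. Where Sections 5.9.1 and 5.10.1 call the 2HG method validated, they mean the LC-MS/MS assay.

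On numbers, Section 9.5 says "it is reasonable to expect at least 10 patient samples per timepoint/technique to interpret potential trends". Section 9.3 says "Both untreated and pre-treated cohorts will be evaluated independently from the statistical perspective" and "AML and MDS patients will also be analyzed separately". The cohort table in Section 9.1.1 gives 39, 14, 39 and 12 patients.

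**The concern.** The maximum of an empirical curve is never below the height of the true curve on average, and it usually lies above it. A cut-off picked at that maximum fits the noise in the sample as well as any signal. Accuracy read off at the same point, in the same patients, is therefore too high, and the excess grows as the sample shrinks.

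The reach is limited but not nil. Section 5.7 classes plasma 2HG as an integrated, mandatory potential biomarker of response. Section 2.4.2.1 wants it followed as a marker of response and progression. Section 2.4 says that knowledge from the correlative work should inform the design of later trials. An uncorrected cut-off with flattering accuracy would be a poor starting point for that.

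**Working it through.** The plan states no AUC, sensitivity, specificity, Youden index or power for this analysis, so there is no planned figure to reproduce. The check asks what the planned rule returns when 2HG carries no information.

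**Inputs.** Sample sizes: 10 (the floor in Section 9.5); 12, 14 and 39 (cohorts in Section 9.1.1); and 94 (stated total) or 39 + 14 + 39 + 12 = 104 (sum of the cohort table). The two totals do not agree, so both are used. Responder counts are assumptions, mostly near 30 to 35%, within the 5% to 50% spanned by the null and alternative rates in Section 9.1.1.

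**Formula.** J = max over cut-offs of (sensitivity + specificity - 1). With delta-2HG independent of response the true value is 0. Under that null the result depends only on ranks, so no distributional form matters, provided there are no ties.

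**Null results** (40,000 simulated data sets per row). Fixed means the direction of the rule is set in advance; free means the better direction is taken from the data.

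| Patients (responders) | Mean J, fixed | Mean J, free | Mean sens/spec, fixed | Chance J is 0.5 or more, fixed/free |
|---|---|---|---|---|
| 10 (3) | 0.345 | 0.516 | 0.692/0.653 | 27%/54% |
| 10 (5) | 0.307 | 0.462 | 0.547/0.760 | 18%/36% |
| 12 (4) | 0.309 | 0.460 | 0.604/0.705 | 26%/51% |
| 14 (5) | 0.290 | 0.429 | 0.651/0.639 | 11%/23% |
| 39 (12) | 0.193 | 0.279 | 0.621/0.572 | 1%/2% |
| 94 (28) | 0.131 | 0.186 | 0.588/0.544 | <0.1%/<0.1% |
| 104 (31) | 0.125 | 0.177 | 0.583/0.543 | <0.1%/<0.1% |

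As a cross-check on the first row, 3 responders among 10 can be ranked in C(10,3) = 120 equally likely ways. Listing them all gives an exact mean J of 0.345 (fixed) and 0.517 (free). Other responder counts give similar fixed-direction values: 0.32 for 4 of 10, 0.33 for 3 of 14 and 0.18 for 17 of 39.

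**Does bootstrap correction help?** The cut-off search was repeated in 100 resamples of each of 1,500 data sets (direction fixed). The second block assumes a true shift of 1 SD, for which the best achievable J is 0.38.

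| Patients (responders) | True shift | Apparent J | J in new patients | Corrected J |
|---|---|---|---|---|
| 10 (3) | none | 0.341 | 0.000 | 0.187 |
| 39 (12) | none | 0.189 | 0.000 | 0.072 |
| 94 (28) | none | 0.134 | 0.000 | 0.050 |
| 10 (3) | 1 SD | 0.626 | 0.307 | 0.478 |
| 39 (12) | 1 SD | 0.503 | 0.345 | 0.403 |
| 94 (28) | 1 SD | 0.460 | 0.360 | 0.394 |

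Share of bias removed, no shift: (0.341 - 0.187)/0.341 = 45% at 10 patients; (0.189 - 0.072)/0.189 = 62% at 39; (0.134 - 0.050)/0.134 = 63% at 94. With the shift at 10 patients: (0.626 - 0.478)/(0.626 - 0.307) = 46%.

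**Very few responders.** At the 5% null rate for exposed patients, 10 patients include no responder with probability 0.95^10 = 0.60. No ROC curve then exists.

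**The case against.** Four points can be made for the plan, and each stands in part.

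- **Reporting is not promised.** A reader might infer that sensitivity and specificity at the cut-off will be published. Section 9.5.1 says only that a cut-off will be determined. The point therefore applies to accuracy figures if they are quoted.
- **Size matters.** A reader might also infer that a useless marker will look good whatever the sample. It will not. At 39 patients the mean apparent sensitivity and specificity are about 0.6 each, and pooled over about 100 they are close to chance.
- **Ten is a floor for every technique.** Plasma 2HG is mandatory, and patients evaluable for response have finished at least one cycle (Section 9.6.2), so a Cycle 1 difference should exist for most of them. This helps less at late time points, since patients leave treatment on progression (Section 6.3), or if the separate-cohort rule of Section 9.3 carries over to 9.5.1.
- **The tests and the AUC involve no cut-off search.** With 4 responders among 10, an uninformative marker reaches a Youden index of 0.5 or more in 28% of data sets (direction fixed), but does so together with a two-sided Mann-Whitney p of 0.05 or less in only 2%. A reader shown both results would usually be warned. The safeguard is partial, because the plan does not tie the cut-off to the test.

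Finally, the analysis sits under exploratory endpoints. No eligibility, stopping or efficacy rule uses the cut-off, and nothing in the documents commits to carrying it into another trial.

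**Conclusion.** The point holds in a limited form. Choosing the cut-off at the maximum Youden index, with no correction or interval, biases upward any accuracy quoted at it. In absolute terms the excess for an uninformative marker is about 0.3 or slightly more in subsets of 10 to 14 patients, just under 0.2 at 39, and 0.12 to 0.13 at 94 to 104. Taking the direction from the data raises these to roughly 0.43 to 0.52, 0.28 and 0.18 to 0.19. The unspecified time point leaves further room for selection, which was not quantified.

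These sizes rest on assumed responder counts and untied marker values. They do not show that 2HG is uninformative, and they do not touch the primary endpoint. This is a desirable improvement to an exploratory analysis, not a flaw in the trial's main inference.

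**What to change.** Amend Section 9.5.1 as follows.

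1. State in advance the post-treatment time point, the direction of the rule, and whether cohorts are pooled.
2. Report the AUC with a 95% CI as the main result, beside the planned Mann-Whitney tests.
3. Label any cut-off hypothesis-generating. Give optimism-corrected Youden index, sensitivity and specificity, with the whole cut-off search repeated in each bootstrap sample, and a bootstrap interval for the cut-off itself.
4. Report no cut-off below a minimum number of responders set in advance. At about 10 patients the correction removes only about half the bias, so it cannot rescue a very small subset.

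The cost is a few sentences, a little more code and less favourable accuracy figures. Sampling, sample size and trial conduct do not change.
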